The investigator must enter all adverse events, serious adverse events and specific scenarios in the electronic CRF within 24 hours of becoming aware of this event and this applies whether or not the investigator considers the event to be related to a study medication, and the CRO in charge of the study must send it to the Pharmacovigilance Departments following the process specific to each pharmaceutical company as set out in table 4 above.

Furthermore, if the serious adverse event is fatal or life-threatening, the Pfizer/Novartis Pharmacovigilance Departments must be notified immediately, including whatever information is available about the adverse event. This time frame also apples to any new (follow-up) information concerning adverse event or serious adverse event notifications that have already been submitted. In the rare situations in which the investigator is not immediately informed that an adverse event has occurred, the investigator must enter the adverse event or serious adverse event in the electronic CRF within 24 hours of becoming aware of it, and the time when he/she first became aware of this adverse event must be recorded.

In the case of adverse events considered to be serious or that fit into the right column of the table above entitled "Declared to pharmacovigilance" which need to be declared to the Pfizer/Novartis pharmacovigilance departments within 24 hours of becoming aware of them, the investigator must seek and provide all additional information to Pfizer/Novartis within this 24-hour time frame. Furthermore, Pfizer/Novartis can ask an investigator to urgently obtain specific additional follow-up information. This information may be more detailed than what has been logged in the study case report form. In general, this information will include a sufficiently detailed description of the adverse event for a complete medical assessment of the case, and an independent judgement on whether there is a causal link. All relevant information pertaining to the event, such as concomitant treatments or illnesses, must be provided. If the patient dies, a summary of the available autopsy results must be sent to Pfizer/Novartis or to the approved representative as soon as possible.

Note: For any death entered in the electronic CRF without an associated SAE being declared, the Pfizer/Novartis Pharmacovigilance Departments will be notified immediately and the investigator will be asked for additional information.

Notification period

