- The test result is considered to be an adverse event by the investigator or the sponsor Simply needing to repeat an abnormal test, in the absence of the above conditions, does not constitute an adverse event. Any abnormal test result that turns out to be due to an error does not need to be reported as an adverse event.

Serious adverse events

A serious adverse event is defined an unwanted medical effect occurring in a patient receiving a medication or nutritional product, regardless of the dose, that:

- Leads to death
- Is life-threatening
- Requires hospitalisation of the patient or prolongs a hospitalisation (see below for the circumstances in which this does not constitute an adverse event)
- Leads to a persistent or significant incapacity (substantial disruption to the ability to conduct acts of daily living)
- Leads to a congenital anomaly or birth defect

Progression of the malignancy over the course of the study (including signs and symptoms of progression) must not be reported as a serious adverse event, unless this results in death during the study or during the adverse events notification period. Hospitalisation due to the signs and

final version of 17/07/2018

symptoms of disease progression must not be reported as a serious adverse event. If the malignancy results in death during the study or adverse events notification period, then the event leading to death must be recorded as an adverse event, and as a grade 5 serious adverse event.

An event will be defined as a medically important event on the basis of medical and scientific judgement. A medically important event is not immediately life-threatening and/or does not lead to death or hospitalisation. However, if it is established that the event may jeopardise the patient and/or require an intervention in order to avoid the outcomes outlined above, the medically important event must be reported as serious.

For example, this category of medically important events would include allergic bronchospasm requiring intensive care in the emergency department or at home, blood dyscrasias, convulsions that do not lead to hospitalisation, or even the development of dependence on a medication or abuse of a medication.

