It is important to note that statistical comparisons in the strictest sense between the different treatment groups in this observational study are not appropriate due to the expected bias and because the groups are not comparable at enrolment (treatments not assigned randomly). If, however, comparisons are envisaged, a multivariate Cox model will be used in order to adjust for patient characteristics that may potentially be associated with the type of treatment received and survival and that could be liable to skew the estimates (confounding factors, effect modification).

 Safety of the treatments (targeted therapies and other treatments) during the prospective phase of the study, defined by instances of treatment discontinuation and the reasons for this, adverse events (graded according to the 'Common Terminology Criteria for Adverse Events' (CTCAE) version 4.0 of May 2009), and any complications of adverse events.

The proportion of patients for whom adverse events are reported (total proportion and proportion reporting grades 3 or 4 adverse events) will be estimated as well as the proportion who stop treatment due to an inability to tolerate it.

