5.7.2. Adverse Events

The numbers and percentages of patients with the following characteristics will be shown overall, and by group at inclusion during the study (targeted therapy/other treatments). We will also show the results by treatment being received at the time of inclusion and during the study: everolimus/sunitinib/chemotherapy/somatostatin analogs etc.

- at least one adverse event,
- at least one serious adverse event,
- at least one adverse event with a suspected relationship with the study treatment,
- an adverse event which was fatal,
- at least one adverse event resulting in permanent discontinuation of treatment,
- at least one adverse event resulting in dosage adjustment/temporary discontinuation of treatment.

- at least one adverse event with a suspected relationship with the study treatment leading to permanent discontinuation of the treatment,
- at least one adverse event with a suspected relationship with the study treatment leading to a dosage adjustment/temporary discontinuation of treatment,
- at least one serious adverse event with a suspected relationship with the study treatment leading to permanent discontinuation of the treatment,
- at least one serious adverse event with a suspected relationship with the study treatment leading to a dosage adjustment/temporary discontinuation of treatment.

The same information will be produced for grade ≥ 3 adverse events.

The following information will also be shown:

- at least one grade 3 adverse event,
- at least one grade 3 serious adverse event,
- at least one grade 3 adverse event with a suspected relationship with the study treatment,
- at least serious grade 3 adverse event with a suspected relationship with the study treatment,
- at least one grade 4 or higher adverse event,
- at least one grade 4 or higher adverse event with a suspected relationship with the study treatment.

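### The SAP omits the protocol's grade 3 or 4 adverse-event proportion; the rows offered instead include tumour deaths coded grade 5, and SAP 5.8 does not declare the change

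*SAP*

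**What the plan says.** Safety is one of the three parts of the primary objective (Protocol 3.1; SAP 5.5). Protocol 8.3.2.1 defines the adverse-event summary as "total proportion and proportion reporting grades 3 or 4 adverse events". Grade 5 is outside that cut.

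SAP 5.7.2 lists a set of patient-level rows (any event, serious, suspected-related, fatal, leading to discontinuation or dose change) and then says "The same information will be produced for grade ≥ 3 adverse events". It adds "at least one grade 3 adverse event" and "at least one grade 4 or higher adverse event", each with a suspected-related counterpart. The shell of Table 14.3.2.2 follows this, and the tables by system organ class and preferred term use grade 3 and grade ≥4. SAP 5.8, which records changes from the statistical part of the protocol, mentions only the confidence-interval formula for survival.

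Protocol section 7 (Serious adverse events) keeps progression out of serious-event reporting unless it is fatal. If the malignancy causes death during the study or the notification period, "the event leading to death must be recorded as an adverse event, and as a grade 5 serious adverse event". Section 7 also provides a follow-up query: "For any death entered in the electronic CRF without an associated SAE being declared", the pharmacovigilance departments are told and the investigator is asked for more information. On the anticipated end of study form, the deceased box points to the safety section of the CRF.

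**The concern.** Two things combine. First, a measure that the protocol names under its primary objective is absent from the planned tables, without a declaration. Second, the substituted cuts are open at the top, and this protocol puts tumour deaths at the top. A cut at grade 3 or 4 leaves those entries out; cuts at ≥3 and ≥4 bring them in, as do the serious and fatal rows. Nothing in SAP 5.7 separates them.

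At stake is what the safety percentages describe. To the extent that they count tumour deaths, they restate overall survival, which is already a separate part of the primary objective. The protocol itself expects the treatment groups to differ at enrolment, so the share of tumour deaths in these rows may differ between columns for reasons unrelated to the drugs.

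**Working it through.** **Which rows contain grade 5**

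| Row (all-causality) | Grade 3 | Grade 4 | Grade 5 |
|---|---|---|---|
| Protocol 8.3.2.1: grade 3 or 4 | yes | yes | no |
| SAP: grade ≥3 | yes | yes | yes |
| SAP: grade 3 alone | yes | no | no |
| SAP: grade ≥4 | no | yes | yes |

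No SAP row matches the protocol's row.

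**Can it be recovered from the planned rows?** Let A be the patients with a grade ≥3 event, F those with a fatal event (taken as grade 5) and G3 those with a grade 3 event. The number with a grade 3 or 4 event is A minus those whose only grade ≥3 event is grade 5. That last group has at most F members, so the target lies between max(A − F, G3) and A. Illustration with 75 patients: 30 with a grade 3 or 4 event (40%), 15 tumour deaths coded grade 5 (20%), independence, no other fatal event. Then A = 30 + 15 × 0.60 = 39 and F = 15. If G3 is 24 or fewer, the tables place the answer between 24 and 39 patients (32% to 52%), where the truth is 30.

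**Size.** The documents state no adverse-event or tumour-death rate, so there is no planned figure to reproduce. With p the true grade 3 or 4 proportion, d the share of patients with a tumour death coded grade 5, and independence assumed:

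P(grade ≥3) = p + d(1 − p)

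| p (assumed) | d (assumed) | Grade ≥3 row | Extra patients of 75 |
|---|---|---|---|
| 40% | 5% | 0.40 + 0.05 × 0.60 = 43% | 2.3 |
| 40% | 10% | 0.40 + 0.10 × 0.60 = 46% | 4.5 |
| 40% | 20% | 0.40 + 0.20 × 0.60 = 52% | 9.0 |

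For the grade ≥4 row, with an assumed true grade 4 proportion of 10%, the same formula gives 14.5%, 19% and 28%.

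**Sensitivity to independence.** If every patient who dies of tumour already had a grade 3 or 4 event, the grade ≥3 row stays at 40%. If none had, it reads 45% to 60%.

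**Scale.** The plan's own 95% half-width for a proportion at n = 75 reproduces: 1.96 × √(0.5 × 0.5/75) = 11.3 points at 50%, and 11.1 points at 40%. The assumed excess of 3 to 12 points runs from well inside that half-width to slightly beyond it.

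**Where it applies.** SAP 9.4.2 shows the two overview tables (14.3.2.1 and 14.3.2.2) both by treatment at inclusion and by treatment received. The tables by preferred term are shown only by treatment received, where fatal and serious events count up to 28 days after stopping. No such window is stated for the tables by treatment at inclusion, so the effect sits mainly there.

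**The case against.** A reader might infer that the plan reports disease mortality as severe drug toxicity. The documents do not support that. The rows are labelled as adverse events of any cause, and SAP 5.7.2 sets suspected-related rows beside them at grade ≥3, grade 3 and grade ≥4. A tumour death judged unrelated enters none of those. The exception is missing causality, which SAP 5.7.2 counts as related.

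Nor is cause of death lost. Table 14.1.3.4 divides deaths in the safety set into disease progression and adverse event by treatment group, Listing 16.2.12 gives the reason for each death, and Table 14.3.2.15 shows fatal events by preferred term. Listing 16.2.8 carries the grade of each event, so someone holding it could count grade 3 or 4 patients by hand. All of this stands. But none of it tabulates the protocol's measure or changes a percentage in the overview tables.

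It is also tempting to fix the size from the 38-month median survival cited in the protocol's introduction: 1 − 0.5^(24/38) = 35.5% dead at two years. That figure describes patients with pNET generally, not this cohort from the start of a treatment line, and the exponential shape is an assumption. The French data cited beside it do not follow one: 61.3% at one year would imply 0.613^5 = 8.7% at five years, against the 44.2% quoted. Not every death is a tumour death, either.

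Collection may be narrower too. Protocol 5.2.2 ends safety collection 28 days after treatment stops, whereas section 7 speaks of death during the study. The query on unreported deaths does not itself create a grade 5 entry, and on the end of study form disease progression is listed as a cause apart from adverse event. These points lower the likely number of such entries; they do not remove the coding rule.

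Finally, the protocol regards strict between-group comparison as inappropriate, and no test or decision rests on these rows. That limits the consequence to description, which is nevertheless the study's purpose.

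**Conclusion.** The point holds as an undeclared omission of a protocol-specified safety measure, made worse by a coding rule that puts tumour deaths into the rows offered in its place. The planned tables only bound the missing patient proportion.

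The amount by which mortality enters the all-causality rows cannot be derived from the documents. The 43% to 52% reading of the grade ≥3 row rests on three assumptions: a true grade 3 or 4 proportion of 40%, tumour deaths coded grade 5 in 5% to 20% of patients, and independence. With complete overlap the excess is zero. Proportionally, the grade ≥4 row is the more exposed, because its base is smaller.

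The suspected-related rows are largely unaffected, and the tables by treatment received are affected less. A claim that one group would be shown as more toxic goes beyond what the documents establish.

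**What to change.** In SAP 5.7.2 and Table 14.3.2.2:

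1. Add a patient-level row for at least one grade 3 or 4 adverse event, all-causality and suspected-related, identified as the protocol's measure.
2. Show grade 5 or fatal events in a separate row, split into death from disease progression and other, using the cause-of-death field on the anticipated end of study form.
3. Footnote the grade ≥3, grade ≥4 and serious rows, in Table 14.3.2.1 as well where they appear, to say that they include progression deaths.
4. List in SAP 5.8 any departure from the protocol's cut that is kept.

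Parallel versions of every row with progression deaths removed are optional. The cost is a few table rows and some SAP wording. The end of study form already collects cause of death, and reporting to pharmacovigilance does not change. The downside is small: the investigator assigns the cause of death, and deaths known only from the adverse-event record (SAP 5.7.3 allows for these) need a stated rule or a cause-unknown category.

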3.3 Therapeutic management since last tumour assessment

Since the last documented visit, the cancer treatment may have been continued or may have changed on one or more occasions. The participating doctor must enter all of the cancer treatment lines prescribed to the patient, and then complete the corresponding screens.

then complete the corresponding screens.		
Therapeutic management since the last documented tumour assessment visit on [date of the last documented visit] and up to and including today's visit:		
If a treatment was "ongoing" at the end of the previous visit (will be checked by the eCRF): Treatment with [name of treatment] that was ongoing at the previous visit continued If treatment continued: Is [combined treatment entered] being continued? If no, reason for stopping [combined treatment entered]: Adverse event* Patient's decision Doctor's decision Other, please state:		
Have any new combined treatments been started since the last visit? $\ \square$ Yes $\ \square$ No		
If yes, which ones? A somatostatin analogue Please state: Careotide Lanreotide Other treatment, please state: 2)		
☐ Treatment with [name of treatment] that was ongoing at previous visit stopped definitively		
If stopped, Date stopped definitively (see Table 5) Reason for stopping treatment (see Table 5) Was [combined treatment entered] still ongoing on the date when [name of the treatment line stopped] was stopped?		
Has a new treatment line been put in place? ☐ Yes ☐ No If yes, please describe all new lines of cancer treatment put in place since the last tumour assessment visit, including the treatment in place at the end of today's visit (see Table 5). If No, if a period of treatment abstention is extended, the patient continues to be followed for 2 years as planned (unless deceased or lost to follow-up).		
If no treatment was "ongoing" at the end of the previous visit (will be checked by the eCRF): Treatment abstention extended (apart from temporary treatment interruptions) If Extended, if a period of treatment abstention is extended, the patient continues to be followed for 2 years as planned (unless deceased or lost to follow-up). New treatment line resumed If Resumed, please describe all new lines of cancer treatment put in place since the last tumour assessment visit, including the treatment in place at the end of today's visit (see Table 5).		

Observational study protocol $final\ version\ of\ 17/07/2018$

Table 5 – Therapeutic management				

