5.7. Safety

Safety assessment criteria will be used to:

- Treatment discontinuations and reasons for this,
- Adverse events and any complications recorded prospectively (graded according to the 'Common Terminology Criteria for Adverse Events' (CTCAE) version 4.0, dated May 2009).

These criteria will be shown descriptively in the safety analysis set.

The analyses of adverse events will be performed twice on the safety analysis set:

- by treatment group at inclusion;
- by group in which treatment was received at least once during the study. In this analysis, the AE will be attributed to ongoing treatment at the start of the AE. An AE beginning after a treatment was discontinued could be attributed to the treatment depending on the rules shown in the table below.

Prior to the safety analysis, the number of patients who received the treatment at least once in the group (targeted therapy/other treatments) and in the treatment subgroups will also be presented. Exposure for each treatment group and subgroup will be calculated.

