The adverse events will also be described by treatment group, in patients who received treatment at least once during the study (targeted therapies/other treatments; the other treatments will also be described depending on whether these involved chemotherapy/somatostatin analogs/others) by System Organ Class (SOC) and Preferred Term (PT). The same analysis will be presented for adverse events with a suspected relationship with the study treatment, grade 3 adverse events with a suspected relationship with the study treatment, serious grade 3 adverse events with a suspected relationship with the study treatment, adverse events grade =3, adverse events ≥4, for serious adverse events, non-serious adverse events, serious grade =3 adverse events, adverse events which resulted in temporary discontinuation of treatment, adverse events which resulted in permanent discontinuation of treatment and adverse events which resulted in the death of patient.

In terms of the analysis by treatment received during the study, several rules have been defined:

The denominator will be the number of patients who received the ongoing treatment during the prospective period at least once. In the case of combination treatments, the treatments will be separated and the patient will be counted several times.

The AE will be deemed to be on treatment until 28 days after the treatment is stopped. Similarly, if the investigator links an AE to a treatment, this will also be counted on this related treatment (regardless of the dates the treatment is taken).

If the treatment is still ongoing at the time of last news, the AE will be deemed to be on treatment for up to 28 days after the date of last news.

Amongst the "other" treatments, Lutathera treatment will be deemed to be metabolic radiotherapy.

If the date of onset of the adverse event is missing:

- If the day of the event is missing, the event will be attributed to all treatments received during the month when the AE was declared.
- if the day and month of the event are missing, the event will be attributed to all treatments during the year in which the AE is declared unless the treatment was received after the end of the AE.

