For combination treatments, the start and end date of the combination were not recorded in the CRF. The visit immediately before the report of the additional combination will therefore be deemed to be the start date and the visit corresponding to discontinuation of the combination will be deemed to be the end date of the combination, unless the combination began or finished during a treatment line (where start and end dates are reported). The 28-day rule also applies to combination treatments.

The AEs will be analysed as follows:

	Actual exposure	Actual exposure +28 days	Treatment reported in the "Causality with the study treatment" column
At least one adverse event		X	
At least one serious adverse event		X	
At least one adverse event with a suspected relationship with the study treatment			X
At least one adverse event resulting in death		X	
At least one adverse event leading to permanent discontinuation of treatment	X		
At least one adverse event leading to change in dosage/temporary discontinuation of treatment	X		
At least one adverse event with a suspected relationship with the study treatment leading to permanent discontinuation of treatment	X		X
At least one adverse event with a suspected relationship with the study treatment leading to adjustment of dosage/temporary discontinuation of treatment	X		X
At least one adverse event with a suspected relationship with the study treatment leading to temporary discontinuation of treatment	X		X
At least one serious adverse event with a suspected relationship with the study treatment leading to permanent discontinuation of treatment	X		X
At least one serious adverse event grave with a suspected relationship with the study treatment leading to adjustment of dosage/temporary discontinuation of treatment	X		X
At least one serious adverse event with a suspected relationship with the study treatment leading to temporary discontinuation of treatment	X		X

^{*} AEs on treatment analysed as reported in the actual exposure and in the "causality with the study treatment" column.

Adverse events will be listed overall, together with the grade ≥ 3 adverse events, serious adverse events, adverse events with a suspected relationship to the study treatment leading to permanent discontinuation of the treatment and adverse events with a suspected relationship to the study treatment leading to temporary discontinuation of the treatment.

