6.2. Measurement Bias

A priori, measurement bias should be minimal, particularly as the study principally involves descriptive objectives and as patient inclusion and data collection will be prospective. Bias may however be present in patients who started treatment (targeted therapy or other treatment) before their inclusion in the study. In these patients, the data will be collected retrospectively until the start date of the ongoing treatment line for the primary objectives of estimating the progression-free survival rate and overall survival rate. This information, which is recorded (progression/response, ongoing treatment) however represents key data in terms of patient survival, which needs to be correctly entered into the patient dossiers. Furthermore, the detailed retrospective collection of response and treatment will only include the treatment which was ongoing at the time of inclusion. The information collected about potential treatment lines prior to inclusion only includes the number of lines and corresponding treatment regimens (not shown).

The estimate of progression-free survival will be less precise than in a clinical trial because of the time intervals between the assessment visits, which are based on real-world conditions and are longer than in clinical trials. Similarly, the assessment of progression/response will be based on the investigator's opinion (which itself will be based on RECIST 1.1 criteria).

The analysis of AEs related to treatment will be partially incomplete for a combination of treatments: the doctor can only enter a single treatment into the CRF and cannot enter which treatment was involved in an action (discontinuation, reduction/increase in dosage).

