8. KEY E-CRF DATA

The table below shows the data required in the eCRF to conduct the main study analysis. As stated in the part describing this analysis (See Section 5.5), particular attention will be paid to recording data on disease progression in the study patients in order to reduce bias.

Parameter	Data	eCRF Variables
Group (documented treatment in	Main treatment	ITTTRTC
the study)	Precision	EVESUNC
Start date (of line ongoing at the	Treatment start date	TSUINDT
time the patient was included) of		TINITDT
treatment with targeted therapy or other treatments		TCHINDT
Disease outcome	Response to treatment, date	Tumour assessment visits:
		Radiological response:
		EXTRESP
		EXTP1DT
		Clinical response:
		EXTCRYN
		EXTCRSP
		EXTP2DT
		Dropped out of study:
		STTRESP
		STTREDT
	Death, date	Dropped out of study:
		STTSTAT
		STTDTDT
Patient status at the end of the	Patient status	Dropped out of study:
study	2-year follow-up completed	STTSTAT
		Complete follow-up:
		VISLVYN
Total duration of exposure to	Treatment start date	TSUINDT
treatment		TINITDT
		TCHINDT
	Treatment end date	FTTEND
	(permanent discontinuation)	
Temporary discontinuations	Discontinuation	TSUTSYN, TEVTSYN, TIXTSYN, TCHTSYN,
		TASTSYN, PTST2YN
	Date discontinuation started	TSTOPDT
	Reason for discontinuation	TSTOPRS
	Duration of discontinuation	TSTOPDU
Permanent discontinuations	Date of permanent discontinuation	FTTEND

Parameter	Data	eCRF Variables
	Reason for permanent discontinuation	FTTENRS
Adverse events	Description	AEVTERM
	Seriousness	AEVSERC
	Relationship with treatment	AEVRELC
	Death	AEVAES1
	Action on treatment	AEVACTC
	Grade	AEVGRAD

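### By-treatment-received AE tables: an AE that stopped one drug of a combination is also counted as a discontinuation of a drug that was continued, in the rows with no causality condition

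*SAP*

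**What the plan says.** SAP 5.7 runs the AE analyses twice: by treatment at inclusion and by treatment received at least once during the study. In the second, "the AE will be attributed to ongoing treatment at the start of the AE". For combinations, SAP 5.7.2 says "In the case of combination treatments, the treatments will be separated and the patient will be counted several times".

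The attribution table at the end of SAP 5.7.2 sets the basis for each row. The row "At least one adverse event leading to permanent discontinuation of treatment" is marked under actual exposure only, and so is the row for dosage change or temporary discontinuation. The versions restricted to a suspected relationship carry a second mark, under the causality column. The table's footnote reads "AEs on treatment analysed as reported in the actual exposure and in the 'causality with the study treatment' column".

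SAP section 8 lists one AE variable for the action taken, "Action on treatment" (AEVACTC), with no drug attached. SAP 6.2 says that the doctor can name only one treatment and "cannot enter which treatment was involved in an action". It concludes that the analysis of treatment-related AEs will be partly incomplete for combinations.

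The CRF in the protocol holds more. Section 3.3 (Therapeutic management) asks at each visit whether the main treatment continued. If it did, the form asks whether the combined drug continued and, if not, the "reason for stopping [combined treatment entered"], with adverse event as an option. If the main treatment stopped, Table 5 takes its date and reason, and the form asks whether the combined drug was still ongoing on that date.

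**The concern.** Exposure at onset is a reasonable basis for counting that an AE occurred under a drug. It is a poor basis for counting that the AE led to that drug being stopped, because a stop is something done to one drug. Once a combination is split and a single action code is carried to every component, the row no longer measures what its label says.

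The typical case is a targeted drug or chemotherapy given with a somatostatin analogue. The analogue belongs to the other-treatments group when it is tabulated separately, so the false count crosses between the two main groups as well as between drugs. A reader of the analogue column would take it as a rate of AE-related discontinuation of analogues, although some of those patients never stopped one.

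**Working it through.** The plan states no figure on this point, so there is none to reproduce. The check follows the counting rule through three cases and compares it with what CRF section 3.3 and Table 5 would show. Each case is a patient on everolimus plus lanreotide whose AE is coded as a definitive stop, with both drugs ongoing at onset.

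| Case | SAP row: everolimus / analogue | CRF stop records: everolimus / analogue |
|---|---|---|
| A. Everolimus stopped for the AE, lanreotide continued | 1 / 1 | 1 / 0 |
| B. Lanreotide stopped for the AE, everolimus continued | 1 / 1 | 0 / 1 |
| C. Both stopped, everolimus for the AE | 1 / 1 | 1 / not resolved |

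- **Case A.** Table 5 gives the everolimus stop date and reason, and section 3.3 records lanreotide as still ongoing. The analogue count is false, and the CRF shows it.
- **Case B.** The main treatment continued, so section 3.3 records a reason for stopping the add-on. The everolimus count is false, and the CRF shows it.
- **Case C.** Section 3.3 records that the add-on was no longer ongoing but asks no separate reason for it. The analogue count may be right or wrong.

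Combination dates make the set of drugs deemed ongoing wider than it was. They were generally not recorded, so SAP 5.7.2 takes the visit before the add-on was reported as its start and the visit reporting its end as its stop. The planned footnote to Table 14.3.1.3 accepts that exposure to combinations is overestimated.

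**Outputs affected.** Tables 14.3.2.1 (all grades) and 14.3.2.2 (grade 3 or higher) contain the two row types without a causality condition. Tables 14.3.2.13 and 14.3.2.14 list by SOC and PT the AEs leading to temporary and permanent discontinuation, by treatment received, and fall under the same rule.

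**Illustration only.** For case A in the analogue column, false counts = n × c × s:
- n = 75, the planned minimum of targeted-therapy patients (SAP 3.3);
- c = share of them also on an analogue, assumed 20% to 60%;
- s = share of those whose targeted drug is stopped for an AE while the analogue continues, assumed 10% to 30%.

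Low: 75 × 0.20 × 0.10 = 1.5, among 15 combination users. Middle: 75 × 0.40 × 0.20 = 6.0, among 30. High: 75 × 0.60 × 0.30 = 13.5, among 45. With the drug's own stop record as the criterion, all three become 0. The documents give neither c nor s.

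**The case against.** **No sentence says that stopping one drug counts as stopping all.** The sentence on splitting combinations directly follows the denominator rule. This is true, and the over-count is an inference from three rules and one field. But nothing in SAP 5.7, 5.7.2 or section 8 limits the numerator to the drug acted on, and SAP 6.2 says the AE page cannot do so.

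**The limitation is disclosed.** In part. SAP 6.2 concerns AEs related to treatment and calls the result incomplete. The affected rows do not require relatedness, and their error is excess.

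**The suspected-relationship rows protect the reader.** They do if the two marks mean that both conditions must hold, which the footnote suggests. But 5.7.2 also adds related AEs whatever the treatment dates, so the SAP should say whether the marks mean and or or.

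**The CRF cannot do everything.** This stands. A reader might infer that it records a stop and a reason for every drug, so that a simple merge would settle the matter. It does not. The add-on has a reason in section 3.3 only if the main treatment continued. The documents show no key from a stop reason to a particular AE, which the AE-count, grade 3 or higher and SOC/PT outputs need. It is also unclear whether an add-on has its own dose-change or interruption screen.

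**The primary safety objective is served elsewhere.** This also stands. A reader might infer that its component on discontinuations and their reasons is compromised. That component is reported under SAP 5.7.1, in Tables 14.3.1.5 to 14.3.1.8, by main treatment and from the stop and interruption records, without the AE attribution rule. SAP 5.9.5 separately reports toxicity stops of the main treatment line.

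**Conclusion.** The point holds within limits. In the by-treatment-received tables, the rows for AEs leading to permanent discontinuation and to dosage change or temporary discontinuation, where causality is not required, over-count for combinations. SAP 6.2 misdescribes this as incompleteness. For permanent stops, the records already collected resolve the cases where one component stopped and the other continued.

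The AE tables by treatment at inclusion, the suspected-relationship rows and Tables 14.3.1.5 to 14.3.1.8 are not affected in the same way. The study is also descriptive and disclaims strict treatment comparisons, which limits the consequence of a narrowed difference between drugs.

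The size cannot be derived from the documents. A reader might infer a distortion of about 3 to 14 percentage points in the analogue column (1.5/45 = 3.3%; 9.4/68 = 14%). Those figures need an assumed 30 patients on an analogue as main treatment, 20% to 50% of 75 targeted-therapy patients on a combination, a 10% to 25% AE-stop rate, and the analogue continuing every time. None of these is in the protocol or SAP. The counting error itself depends on none of them.

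**What to change.** In SAP 5.7.2, for the by-treatment-received rows without a causality condition:

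1. Count an AE coded as a definitive stop under drug X only if CRF section 3.3 or Table 5 shows that X itself was permanently stopped at or after the AE onset. Match by stop date for the main treatment and by visit interval for an add-on. Require adverse event as the stop reason wherever a reason is recorded.
2. Do not count it under a component recorded as continued or still ongoing.
3. Where both components stopped and the add-on has no recorded reason, keep the count and footnote that the action may concern another component. Do the same for dose changes and interruptions where no drug-specific screen exists for the add-on.
4. State whether two marks in the attribution table mean that both conditions must hold or that either is enough.
5. Amend SAP 6.2 to say that these rows may over-count for combinations.

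The cost is SAP wording and some extra programming, with no new data collection. Matching AEs to stops takes more work for the AE-count, grade 3 or higher and SOC/PT outputs than for the all-grade patient row. It will be approximate for add-on drugs, whose stops are known only to the visit interval.
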